9.2 Analyses Plans

At the time of the imaging study, each scan will be interpreted by a nuclear medicine physician, who will be fully cognizant of the clinical, imaging and laboratory data. Focal uptake on choline PET will be reported by location (left/right, location with respect to the thyroid, or description of location if atypical), along with measured SUVmax. These reads will not be used for evaluation of the primary endpoint.

9.2.1 18F-fluorocholine blinded reads

All 18F-fluorocholine imaging data will be anonymized and collected. PET data will be interpreted by three different board certified nuclear medicine readers in a random order at separate reading sessions. Prior to interpretation a training data set using choline PET studies not included in the study will be used to train the readers. Clinical information will not be available to the readers at time of interpretation. Cross sectional imaging from the PET will be available for anatomic correlate, but no other imaging study will be available. Each study will be characterized by location (left/right, location with respect to the thyroid, or description of location if atypical). "Atypical" refers to adenomas that are not in the thyroid bed and would include the mediastinum. All suspected lesions as well as the single most suspicious lesion will be recorded. For example, in the setting of multiple parathyroid adenomas, one lesion will be reported by the readers as most suspicious.

The location of each adenoma that is surgically confirmed will be marked in the identical fashion (left/right, location with respect to the thyroid [ie inferior or superior], or description of location if atypical). For each reader, lesions will be characterized as follows:

1. True positive: Location of the suspected adenoma on FCH PET correlates with location of an abnormal parathyroid at time of surgery. For a patient with multiple hyperplastic glands, only one gland needs to correlate for the patient to count as a true positive.
 - a. For analysis, adenomas described as arising in the mid thyroid bed will be considered correct if located in either the inferior or superior bed.
2. False positive: Location of the suspected adenoma on FCH PET does not agree with location of an abnormal parathyroid at time of surgery.
3. True negative: There are no true negatives as patients with primary hyperparathyroidism have near 100% incidence of hyperplastic adenomas.
4. False negative: No evidence of parathyroid adenoma on FCH PET independent of findings at time of surgery.

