9.1 Statistical Design

We will enroll a total of 140 patients (65 in our initial cohort, on which the sample size estimate is based). The sample size will be based upon comparison to setamibi SPECT (MIBI). Multiple meta-analysis of MIBI SPECT have been performed and demonstrate a sensitivity ranging 79 to 84% for MIBI SPECT (15,16). This detection rate is higher than we see at our institution since we are a referral center for patients who have previously failed parathyroidectomy, where the study has a lower sensitivity. For the purpose of our analysis we will do our sample size assuming a sensitivity of 70%, which mirrors our practice. At an 87% power with an alpha level of 0.05, we estimate that a sample size of 65 patients would be needed, assuming 100% disease prevalence, 70% accuracy of MIBI (sestamibi), an estimated 85% accuracy of FCH PET, and 10% dropout rate.

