9.2.2 Sestamibi evaluation

In patients who had a sestamibi study performed prior to the fluorocholine imaging study, we will use the original dictated report from the sestamibi. This will be done as there may be significant bias in the interpretation of the sestamibi studies if re-interpreted. Identical to the PET data, the study reports, will be used to characterize location (left/right, location with respect to the thyroid, or description of location if atypical). All suspected lesions as well as the single most suspicious lesion will be recorded. The sensitivity from this analysis will be used as our comparator for the FCH PET. For each reader, lesions will be characterized as follows:

1. True positive: Location of the suspected adenoma on sestamibi correlates with location of an abnormal parathyroid at time of surgery. For a patient with multiple hyperplastic glands, only one gland needs to correlate for the patient to count as a true positive.
 - a. For analysis, adenomas described as arising in the mid thyroid bed will be considered correct if located in either the inferior or superior bed.
2. False positive: Location of the suspected adenoma on sestamibi does not agree with location of an abnormal parathyroid at time of surgery.
3. True negative: There are no true negatives as patients with primary hyperparathyroidism have near 100% incidence of hyperplastic adenomas.
4. False negative: No evidence of parathyroid adenoma on sestamibi independent of findings at time of surgery.

The performance of the imaging modalities will be quantified by sensitivity, specificity, positive predictive value and negative predictive value.

Performance will be assessed using surgery as the gold standard with postoperative normalization of calcium as the study endpoint as described above. For this study to have a positive outcome, two of the three FCH PET readers have to have a sensitivity that is 10% greater than that of sestamibi imaging. For statistical analysis we will use the McNemars's test with a p-value of 0.05 for significance. We will also compare the sensitivity of 18F-fluorocholine to the predetermined detection sensitivity of 70%. Again, two of the three FCH PET readers have to have a sensitivity that is 10% greater than 70% (ie 80%). We will also report an interreader variability for the FCH PET reads using a Fleiss's Kappa. The baseline characteristics will be reported as follows: continuous parametric data will be reported as mean

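### Sections 9.2.1 and 9.2.2 do not say which recorded lesion decides a patient's result, and a wrong mark never counts against sensitivity

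*Combined protocol and SAP*

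**What the plan says.** Section 9.2.1 (FCH blinded reads) and section 9.2.2 (sestamibi, taken from the original dictated report) use the same recording rule: "All suspected lesions as well as the single most suspicious lesion will be recorded". The classification that follows is introduced at lesion level: "For each reader, lesions will be characterized as follows".

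- True positive: "Location of the suspected adenoma on FCH PET correlates with location of an abnormal parathyroid at time of surgery". A further sentence makes one matching gland enough for the patient, but only where the patient has several hyperplastic glands.
- "False positive: Location of the suspected adenoma on FCH PET does not agree with location of an abnormal parathyroid at time of surgery".
- True negative: none, by definition.
- False negative: only a scan that shows no adenoma, whatever surgery finds.

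Section 9.2.2 repeats these categories for sestamibi and then sets the analysis: "For statistical analysis we will use the McNemars's test with a p-value of 0.05 for significance". Success requires two of the three FCH readers to have a sensitivity 10% above sestamibi. A second comparison requires two of three to exceed the fixed 70% by 10%, which the plan spells out as 80%. PPV, NPV and specificity are to be reported, with no success criterion. No formula for sensitivity is given.

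**The concern.** Two records are kept per scan, and the rules then score one suspected adenoma, in the singular, without saying which record is meant. The one patient-level sentence deals with several abnormal glands at surgery, not several marks on the scan. Section 1.1 says that over 80% of cases have a single adenoma, so for any such patient with two or more marks the rules are silent.

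This affects the primary result in two ways. McNemar's test pairs one FCH outcome with one sestamibi outcome per patient, and the plan does not define that outcome. In addition, both success criteria rest on sensitivity alone, and nothing in the definitions lets a wrong mark reduce it. A reader who marks more sites therefore carries no risk on the primary endpoint.

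**Working it through.** **1. The plan's own figure.** Section 9.1 gives 65 patients: "At an 87% power with an alpha level of 0.05", with "70% accuracy of MIBI (sestamibi), an estimated 85% accuracy of FCH PET, and 10% dropout rate". The one-sample normal approximation, one-sided, gives

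n = [(1.645·√(0.70·0.30) + 1.126·√(0.85·0.15)) / 0.15]² = 59.4, so 60, and 60/0.90 = 67 after dropout.

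A two-sided McNemar calculation with no pair favouring sestamibi also gives 60 and 67. Either is within two patients of 65, so the figure is broadly reproduced and is not in dispute. It does presuppose one yes/no result per patient. Because it assumes 100% prevalence, its 70% and 85% read most naturally as shares of all patients.

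**2. The rules applied to one patient.** Take one adenoma, left inferior, and two marks, left inferior and right superior. The first mark meets the true-positive definition and the second the false-positive definition. No precedence is stated. If the most suspicious lesion decides, the result depends on which mark was ranked first; if any mark decides, it is a hit. No sentence makes a non-matching mark cancel a match, so the extra mark carries no penalty under either reading. Specificity cannot register it: with no true negatives, TN/(TN+FP) is 0 as soon as one false positive exists. PPV counted by lesion would fall.

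**3. Second marks, all operated patients in the denominator.** Assumptions: four sites (left/right by superior/inferior), one abnormal gland, a wrong mark in every miss, and a second mark placed at random among the three remaining sites in a share q of patients. With h the hit rate of the most suspicious lesion,

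any-mark rate = h + (1 − h)·q/3.

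| h | q = 0.5 | q = 1 |
|---|---|---|
| 0.70 | 0.70 + 0.30·0.5/3 = 0.750 | 0.70 + 0.30/3 = 0.800 |
| 0.85 | 0.85 + 0.15·0.5/3 = 0.875 | 0.85 + 0.15/3 = 0.900 |

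The gain is 5 to 10 points at 70% and 2.5 to 5 points at 85%. If the misses at 70% were instead negative scans, a random mark would have four sites to fall on: 0.70 + 0.30/4 = 77.5%.

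**4. Effect on the FCH minus sestamibi gap, same model.**

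| Second marks | FCH | Sestamibi | Gap |
|---|---|---|---|
| none | 85% | 70% | 15 |
| both scans, q = 1 | 90% | 80% | 10 |
| FCH only, q = 1 | 90% | 70% | 20 |
| sestamibi only, q = 1 | 85% | 80% | 5 |

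**5. The same question under TP/(TP+FN).** In step 3 every miss has a wrong mark, so FN = 0 and the ratio is 70/70 = 100% before and 80/80 = 100% after: no lift. With a mixed, assumed set of 100 operated patients (70 with the most suspicious lesion right; 10 with it wrong but a secondary mark right; 10 with all marks wrong; 10 with no mark):

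- all patients: 70/100 = 70% by most suspicious lesion, 80/100 = 80% by any mark;
- TP/(TP+FN): 70/80 = 87.5% against 80/90 = 88.9%.

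Over all patients, the scoring choice alone decides whether the 80% bar is missed or met.

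**6. Marking otherwise negative scans.** Assume 75 correct, 10 wrong-site and 15 negative. One random mark on each of the 15 gives 75 + 15/4 = 78.75 hits. Over all patients the rate goes from 75% to about 78.8%. TP/(TP+FN) goes from 75/90 = 83.3% to 78.75/78.75 = 100%, because no false negatives remain. This happens even if only the most suspicious lesion counts.

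**The case against.** The classification is introduced for lesions, and a true-positive and a false-positive lesion in one patient is no error in a lesion-level analysis. That is correct; the conflict arises only because the planned test and criteria work per patient. The sentence on multiple hyperplastic glands leans towards an any-match rule, but it does not reach the patient with one gland and several marks.

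A reader might infer that over-calling could supply the whole 10-point margin. The documents do not support that as an expected effect. It needs a random second mark in every patient, a 70% starting rate (the value for sestamibi and the fixed threshold; FCH is planned at 85%), and an all-patient denominator that the plan does not state. Random marking is also a crude model for trained, board-certified readers, and the four-site model leaves out atypical locations and the rule that accepts a mid-bed call at either level.

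A reader might also infer that the gap favours FCH. FCH readers are asked prospectively to list every lesion, whereas sestamibi relies on routine reports, so more marks on FCH is plausible. But no figure for marks per scan is given, the same rule applies to both scans, and equal marking in step 4 narrows the gap. Nor do the documents describe any intention to choose the scoring after seeing results; they simply leave it open.

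**Conclusion.** The concern holds as a missing patient-level rule together with a sensitivity that cannot be reduced by wrong marks. The primary result is not uniquely defined for a patient with one abnormal gland and more than one mark, on either scan.

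The size is conditional. Under the assumptions of step 3, second marks add 2.5 to 5 points at 85% and 5 to 10 points at 70% for q between 0.5 and 1. Under TP/(TP+FN) they add little or nothing, but marks on otherwise negative scans remove false negatives and can take the ratio to 100%. Since the plan states neither the deciding lesion nor the denominator, both need to be settled. All mark frequencies and patient counts used here are assumptions, and neither a bias towards FCH nor its size is shown by the documents. This should be corrected before the reads are scored against surgery.

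**What to change.** In sections 9.2.1 and 9.2.2:

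- Give each patient one mutually exclusive category per reader (hit, wrong site, negative scan), based on the single most suspicious lesion. Count a hit only if that lesion matches an abnormal gland.
- Count wrong-site calls and negative scans both as misses, with all operated, evaluable patients in the denominator. Choosing the most suspicious lesion without this step would leave the effect in step 6 in place.
- Use that hit/miss result in McNemar's test and in both success criteria.
- Apply the same rule to sestamibi, and fix in advance how to score a dictated report that names several sites without ranking them.
- Report any-lesion scoring and the number of marks per patient, for each modality, as supportive results.

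The cost is a few sentences in each section and a short rule for unranked reports. The most suspicious lesion is already to be recorded for both scans, so no new data are needed. The downside is that the stated sensitivities may be lower.

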2.1 Primary objective

To investigate the performance (accuracy) of 18F-fluorocholine PET in the detection of hyperfunctioning parathyroid glands in surgical patients with biochemically proven primary hyperparathyroidism.

3 Study Endpoints

3.1 Primary endpoint 1

Sensitivity and specificity of 18F-fluorocholine PET for the detection of abnormal parathyroid adenomas confirmed by pathology as compared to sestamibi imaging.

3.2 Primary endpoint 2

Sensitivity and specificity of 18F-fluorocholine PET for the detection of abnormal parathyroid adenomas confirmed by pathology as compared to a predefined threshold.

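### Specificity, half of both primary endpoints, and the promised NPV can only be 0% or undefined, because the plan's scoring rules allow no true negatives

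*Combined protocol and SAP*

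**What the plan says.** Section 3.1 sets the first primary endpoint as "Sensitivity and specificity of 18F-fluorocholine PET for the detection of abnormal parathyroid adenomas confirmed by pathology as compared to sestamibi imaging". Section 3.2 sets the second as "Sensitivity and specificity of 18F-fluorocholine PET for the detection of abnormal parathyroid adenomas confirmed by pathology as compared to a predefined threshold". Section 9.2.2 adds: "The performance of the imaging modalities will be quantified by sensitivity, specificity, positive predictive value and negative predictive value".

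The scoring rules are in 9.2.1 for FCH PET and are repeated for sestamibi in 9.2.2. On true negatives, both lists say: "True negative: There are no true negatives as patients with primary hyperparathyroidism have near 100% incidence of hyperplastic adenomas". A false negative on PET is "No evidence of parathyroid adenoma on FCH PET independent of findings at time of surgery", and on sestamibi it is "No evidence of parathyroid adenoma on sestamibi independent of findings at time of surgery". A false positive is a called location that does not match an abnormal gland at surgery.

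The decision rules in 9.2.2 refer to sensitivity only. For a positive outcome, "two of the three FCH PET readers have to have a sensitivity that is 10% greater than that of sestamibi imaging". For the second endpoint, "We will also compare the sensitivity of 18F-fluorocholine to the predetermined detection sensitivity of 70" per cent, with 80% as the hurdle. Section 9.1 sizes the study on 70% against 85% accuracy at 100% disease prevalence.

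**The concern.** Specificity and NPV both have true negatives as their numerator. A plan that fixes that count at zero has fixed both measures before any scan is read, yet it names one of them in each primary endpoint.

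What is at stake is the reported primary result. A literal report would give the same 0% specificity to a reader with one wrong-location patient and to a reader with many. It would therefore say nothing about overcalling, which is what specificity is there to detect. Dropping the measure only when results are reported would be an unplanned change to a primary endpoint.

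**Working it through.** **The plan's own figures.** The documents give no expected value for specificity or NPV. The only design figure that can be computed is the sample size in 9.1: 65 patients, 87% power, alpha 0.05, 10% dropout. With 65 x 0.9 = 58.5, taken as 58 evaluable, a one-sample comparison of 0.85 with 0.70 at one-sided 0.05 has power of 86.2% (normal approximation) or 87.0% (arcsine). The plan does not state the sidedness; one-sided is an assumption that reproduces the figure. The calculation uses no non-diseased unit, so the missing true negatives do not affect it.

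**What the rules imply.** Let TP, FP, TN and FN be the four counts, with TN = 0 by rule.
- Specificity = TN/(TN + FP) = 0/(0 + FP): 0% if FP is 1 or more, 0/0 if FP = 0.
- NPV = TN/(TN + FN) = 0/(0 + FN): 0% if FN is 1 or more, 0/0 if FN = 0.

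No other value is possible, whether lesions or patients are counted. The comparison of specificity in endpoint 3.1 can only be 0% against 0%, or undefined on at least one side. In endpoint 3.2 the only predetermined value is for sensitivity, so specificity has nothing to be compared with.

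**What is lost, on assumed counts.** The plan does not give the number of operated patients. Assume 65, 100 or 140, with 85% correctly localised, and one called lesion in each positive patient so that patient and lesion counts agree. Section 9.1 speaks of 85% accuracy; reading that as the share localised is an assumption made here. Two splits of the remaining patients are compared: (A) one false positive and the rest false negative; (B) all but one false positive. Intervals are 95% Clopper-Pearson.
- N = 65, TP 55, remainder 10. A: PPV 55/56 = 98.2% (90.4 to 100.0). B: 55/64 = 85.9% (75.0 to 93.4).
- N = 100, TP 85, remainder 15. A: 85/86 = 98.8% (93.7 to 100.0). B: 85/99 = 85.9% (77.4 to 92.0).
- N = 140, TP 119, remainder 21. A: 119/120 = 99.2% (95.4 to 100.0). B: 119/139 = 85.6% (78.7 to 91.0).

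Specificity and NPV are 0% in all six cases. PPV separates A from B.

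**The PPV unit matters.** Assume 100 operated patients: 85 with at least one matching call, 5 with only wrong calls and 10 negative. Ten of the 85 each have one extra wrong call, and every other positive patient has a single call.
- Any match counts, per patient: 85/(85 + 5) = 94.4%.
- Per lesion: 85/(85 + 5 + 10) = 85.0%.
- Per patient on the most suspicious lesion: between (85 - 10)/90 = 83.3%, if the wrong lesion is ranked first in all ten, and 85/90 = 94.4%, if it is ranked first in none.

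In the limit, a reader who marks every possible site in every patient reaches 100% sensitivity and 100% PPV on the any-match label. An any-match PPV would therefore not replace what specificity was meant to show.

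**The case against.** The strongest reply is that little depends on this. The plan says openly that it has no true negatives, its success rule and hurdle use sensitivity, and PPV is already listed to capture wrong-location reads. That stands as a limit on the consequence, but it does not remove the contradiction. Specificity is still in both primary endpoints, and PPV is tied to neither. The PPV unit is also unstated, since 9.2.1 announces a lesion-level classification and then gives a patient-level true-positive rule.

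A second reply is that the word 'near' in the prevalence statement leaves room for an occasional true negative. It does not: the same sentence says there are none, and the false-negative rule takes every negative scan regardless of surgery. The plan defines no gland-level or site-level negative that could supply them.

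A third point concerns the remedy. One might treat PPV with an any-match patient label as simply applying the plan's false-positive rule. The text does not support that. The one-gland allowance in 9.2.1 concerns patients with several abnormal glands, not readers who call several sites.

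Someone reading the plan might also infer that the success decision or the sample size is compromised. The documents do not support this, because neither uses specificity or NPV.

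**Conclusion.** The fault is certain, and it is one of endpoint definition. As the rules stand, the specificity part of both primary endpoints and the promised NPV carry no information, for either test, any reader or any N. This follows from the wording and needs no numerical assumption. The PPV figures rest on assumed counts; they show what specificity would hide and do not predict results.

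The plan should be corrected, but the fault does not undermine the sensitivity decision. Whether patients with only wrong-location calls stay in the sensitivity denominator is a separate issue and forms no part of this conclusion.

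**What to change.** Amend the protocol before the blinded reads are analysed. Section 9.1 mentions an initial cohort of 65, and the documents do not say whether its reads have been analysed; if they have, the amendment should disclose it.

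1. Delete specificity from 3.1 and 3.2, and delete specificity and NPV from 9.2.2.
2. Name PPV as the companion to sensitivity, with a 95% CI for each FCH PET reader and for sestamibi. For endpoint 3.1, report it in the patients who have both scans.
3. Report PPV in two ways: per patient, on the lesion ranked most suspicious, which the plan already records for both tests; and per lesion, over all suspected lesions, with an interval that allows for clustering within patient. Do not present an any-match patient label as the plan's own false-positive rule.
4. State as a limitation that a non-matching site may never have been explored, because section 7.1.2 lets FCH PET results help direct surgery.

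The cost is a signed amendment with IRB approval (section 10.4), revised endpoint wording and a small added analysis. No new data and no change in sample size are needed. The downside is that the trial makes no specificity claim. A site-level specificity would be possible only if explored and normal sites were recorded, and the plan marks only surgically confirmed adenomas.

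### Wrong-site calls count as false positives and never as misses, so they leave the sensitivity denominator, inflate both success measures and can rank the two scans in the wrong order

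*Combined protocol and SAP*

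**What the plan says.** Section 9.2.1 sorts FCH PET reads into four categories. A true positive is a call that matches an abnormal gland at surgery; with several abnormal glands, one match is enough for the patient. The other two categories in use are:

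- "False positive: Location of the suspected adenoma on FCH PET does not agree with location of an abnormal parathyroid at time of surgery"
- "False negative: No evidence of parathyroid adenoma on FCH PET independent of findings at time of surgery"

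True negatives are declared not to exist, because practically every patient has disease. Section 9.2.2 repeats the scheme for sestamibi, including "False negative: No evidence of parathyroid adenoma on sestamibi independent of findings at time of surgery".

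On what is scored, both sections record two things: "All suspected lesions as well as the single most suspicious lesion will be recorded". Neither says which of the two decides the category. Definition 1a adds that "adenomas described as arising in the mid thyroid bed will be considered correct if located in either the inferior or superior bed".

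Section 9.2.2 then bases a positive outcome on sensitivity. Two of three FCH readers must exceed sestamibi by 10 points, and two of three must reach 80% against the 70% threshold. For the test, "we will use the McNemars's test with a p-value of 0.05 for significance". Positive predictive value (PPV) is to be reported but is in neither rule. No formula for sensitivity is given. Section 9.1 sizes the study on accuracy of 70% against 85%, at 100% prevalence.

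**The concern.** Every operated patient is taken to have an abnormal gland, so each scan either finds it or does not. The definitions split the failures in two, and only the blank scan counts as a false negative. A scan that points to the wrong place has also failed to find the gland, yet it enters neither TP nor FN.

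Four things follow.

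- **The measure rewards over-calling.** A reader who always marks some site has FN = 0 and scores 1/(1+0) = 100% with a single hit. Turning a blank read into a guess can only raise the score.
- **The denominators differ between scans.** Each scan drops its own wrong-site patients. McNemar's test needs each patient scored as found or not found on both scans, so it does not test the two stated sensitivities.
- **The scoring unit is open.** If any marked lesion can score, a left-mid call plus a right-mid call covers all four thyroid-bed positions under definition 1a.
- **The sample size rests on another quantity.** Accuracy at 100% prevalence is TP over all patients, which counts wrong-site calls as failures.

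Both success rules act on this sensitivity. Section 7.1.2.1 says that the FCH result helps to direct surgery, so a wrong site is the error that matters most, and neither rule penalises it.

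**Working it through.** **Inputs.** From section 9.1: 70% and 85% accuracy, 100% prevalence, 65 patients, 10% dropout, "At an 87% power with an alpha level of 0.05". From section 9.2.2: the 10-point rule and the 80% rule. Assumed, because the documents do not give it: the wrong-site share w, taken over 0 to 25% of operated patients, with one 35% case.

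**The plan's own figure.** 65 × 0.9 = 58.5 evaluable patients. A one-sample test of 0.70 against 0.85 (normal approximation, one-sided 0.05) has power

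Φ{[0.15 − 1.645·√(0.70·0.30/n)] / √(0.85·0.15/n)} = 86.2% at n = 58 and 86.8% at n = 59.

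The plan does not state sidedness. A two-sided McNemar test at the smallest possible discordance (0.15) gives 85.8% to 86.5%. The stated 87% is reproduced in essence. In both calculations 70% and 85% are shares of all evaluable patients, so wrong-site calls count as failures.

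**Formula.** With c the share correctly localised, w the share with only wrong-site calls and 1 − c − w the share with a negative scan:

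- sensitivity from the plan's categories: TP/(TP+FN) = c/(1−w)
- correct localisation: TP/(TP+FP+FN) = c

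**One scan with c = 70%.** The last two columns give the chance that one reader reaches 80% with 58 patients (400,000 simulated trials).

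| w | Reported sensitivity | Smallest c that reports 80%: 0.8(1−w) | Chance, plan's measure | Chance, wrong site counted as miss |
|---|---|---|---|---|
| 0 | 70.0% | 80% | 4% | 4% |
| 5% | 73.7% | 76% | 15% | 4% |
| 10% | 77.8% | 72% | 37% | 4% |
| 15% | 82.4% | 68% | 69% | 4% |
| 20% | 87.5% | 64% | 93% | 4% |

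The 80% bar is met at c = 70% when 0.70/(1−w) ≥ 0.80, that is 1−w ≤ 0.875, so w ≥ 12.5% and negative scans ≤ 17.5%.

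**Two scans, per 100 operated patients (correct/wrong site/negative).**

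| Case | FCH | Sestamibi | Reported | Correctly localised |
|---|---|---|---|---|
| Equal | 70/25/5 | 70/10/20 | 70/75 = 93.3% vs 70/90 = 77.8% | 70% vs 70% |
| Reversal | 70/25/5 | 75/5/20 | 93.3% vs 75/95 = 78.9% | 70% vs 75% |
| Larger reversal | 60/35/5 | 75/5/20 | 60/65 = 92.3% vs 78.9% | 60% vs 75% |

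The reported gaps are 15.6, 14.4 and 13.4 points, so each case clears the 10-point and the 80% thresholds.

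**McNemar's test.** In the equal case the denominators are 75 and 90. A test restricted to patients who are TP or FN on both scans would lose between 25 patients (the wrong-site groups fully overlap) and 35 (25 + 10, no overlap). A test on all 100 patients would compare 70 with 70, not 93.3% with 77.8%.

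**The case against.** The plan writes no formula. Section 9.1 uses 70% both as a sensitivity and as an accuracy, which at 100% prevalence suggests that the authors may have had TP over all patients in mind. That is a fair reading of section 9.1. However, sections 9.2.1 and 9.2.2 define the categories explicitly, and an analyst who applies the textbook formula to them gets the biased measure. Nothing elsewhere corrects it.

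McNemar's test could act as a safeguard. Scored over all paired patients, the equal case has equal discordant counts and cannot be significant, and in the reversal cases the discordance favours sestamibi. This stands as far as it goes. But the paired outcome is undefined, the plan does not say outright that significance is required for a positive outcome, and no test is attached to the 80% rule.

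The wrong-site rates are hypothetical. At w = 5%, 70% becomes only 73.7%. The pilot in section 1.3 found all 8 adenomas where PET pointed, although 8 selected patients cannot settle the rate. Equal w on both scans keeps their order and only stretches the gap by 1/(1−w); reversal needs unequal rates. All of this limits the size, not the defect. Nor does the design make the rates equal: FCH is read by trained, blinded readers, sestamibi from the original dictated reports.

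PPV would reveal wrong-site calls. It would, but it decides nothing.

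**Conclusion.** The concern holds. Followed as written with the standard formula, the plan's sensitivity exceeds the share of patients correctly localised by the factor 1/(1−w). At 70% correct, a wrong-site share of 12.5% is enough to reach the 80% bar. At 15%, one reader's chance of reaching it is about 69% instead of 4%, and with unequal rates the worse scan can appear better.

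This rests on three assumptions: TP/(TP+FN) is the intended formula, w is in the range shown, and 58 patients are evaluable. The chances are for one reader; the two-of-three rule is not modelled. A patient with one correct and one wrong call stays a true positive if any lesion may score, so only patients without a matching call drop out.

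The fault lies in the definitions, not in the sample size figure. Because it can decide whether the trial is declared positive, it must be fixed before analysis.

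**What to change.** In sections 9.2.1 and 9.2.2:

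1. Define the primary measure per patient as correct localisation: true positives divided by all operated patients with a reference result.
2. Count a wrong-site call and a negative scan both as a miss, identically for FCH and sestamibi.
3. Score each patient on the single most suspicious lesion, and say that the unit is the patient.
4. Apply the 10-point rule, the 80% rule and McNemar's test to this found/not-found variable.
5. Report wrong-site calls separately through PPV.

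The cost is mainly wording, since the plan already records the most suspicious lesion for both scans. One addition is needed: a rule, set before scoring, for dictated sestamibi reports that list several sites without ranking them. The reported sensitivities fall by the factor 1−w. Section 9.1 is already sized on this quantity, so this change alone gives no reason to alter the 65 patients.
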